#### Sensitivity analysis

Sensitivity analysis is planned for the outcomes: heavy days, total alcohol intake, 0-days with the following assumptions:

- 1. We assume the drop-out is caused by a relapse in alcohol intake, and therefore we will impute the values of the missing final data for the above categories, as the baseline value and half a baselinevalue.
- 2. We assume the missing data are MNAR and will make a per protocol (PP) analysis.

We assume that the amount of chlordiazepoxide at screening will influence the baseline SCIP and PACS score. We will do a sensitivity analysis and compare the SCIP-results from week 4 with the baseline results, to see if there is a difference.

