## Sample size

The original sample size calculation was performed with an estimated drop-out rate of 40 % and a power of 90%. That led to a total number of 114 patients to include. Please see appendix 1. In May 2019 when recruitment was almost finished, the dropout rate was nearly 60%. We choose as a consequence to do a

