#### Justification of sample size incl. power calculation

The primary outcome measure, i.e. the total number of heavy drinking days, was used for the sample size calculation. Based on data from the study by Johnson et al, where the reduction in the percentage points of the total number of heavy drinking days was 60 pp in the intervention group and 33 pp in the control group. With an alpha of 5%, and a power of 85%, and with an estimated SD of 34.5, the estimated sample size was of 58 patients (29 in each group). With an estimated dropout rate of 60% a total number of 144 patients (72 patients in each arm) was needed (please see below)

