# Statistical Principles

# Confidence and P-values

The level of statistical significance will be with an alpha set at 0.05, two-sided testing, and a confidence interval of 95%. There will be no adjustment for multiplicity.

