### Analysis methods

All continuous outcomes, i.e., change in metabolic parameters, weight, body composition parameters, alcohol use, etc. will be analyzed using ANOVA from baseline to last observation endpoint. Categorical outcomes will be analyzed using chi-square analyses. As the study was conducted as a randomized trial, no covariates adjustment is in principle necessary to assess causal effects.

Edition: 1.0

26.05.20

Statistical Analysis Plan

EudraCT 2016-003343-11

We will use residual plots and qq-plots in combination with Wally plots to validate the normality assumptions of the residuals in the ANOVA models. If the distributional assumption about normality of the residuals does not hold then we will first see if a log-transform of the outcome will result in a model fit that does not appear to violate the assumptions of normality. If the log-transform still does not hold, our next step will be to consider if the lack of fit is caused by inflation, e.g. due to too many observations being zero. Should that be the case we will replace the standard ANOVA model with a zero-inflated gaussian mixture model for the analyses. Should none of these approaches work we will use quantile regression and model the median outcome instead.

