# Missing data

Missing data will be imputed using the multiple imputation method. However, for multiple imputations to work properly we need to assume that the data are missing at random (MAR) which may not be the case in our study. Consequently, as a sensitivity analysis of handling the missing data, we will consider two realistic alternatives for the missing mechanism: 1) to assume that all non-observed individuals at 26 weeks have reverted to their pre-study drinking habit, and 2) that all non-observed individuals at 26 weeks have halved

**EXALT** study

Statistical Analysis Plan

Edition: 1.0

EudraCT 2016-003343-11

their drinking. If only multiple outcomes are missing then we will use a linear mixed-effect model which is an extension of the ANOVA model for analyzing the data.

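### The relapse-imputed data have no named model, and the default fallback models can make the own-baseline scenario uninformative

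*SAP*

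**What the plan says.** Sensitivity analysis in the SAP assumes that drop-out reflects relapse. For heavy drinking days, total intake and alcohol-free days it states: "we will impute the values of the missing final data for the above categories, as the baseline value and half a baselinevalue". Missing data repeats both scenarios as alternatives to multiple imputation; the first is "to assume that all non-observed individuals at 26 weeks have reverted to their pre-study drinking habit". Neither section names the model to be fitted to the completed data.

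The only model rule is in Analysis methods. It covers continuous outcomes and names alcohol use among them. It starts with ANOVA and checks the residuals graphically. If normality fails, a log-transform is tried. If excess zeros are the cause, "we will replace the standard ANOVA model with a zero-inflated gaussian mixture model for the analyses". Finally, "Should none of these approaches work we will use quantile regression and model the median outcome instead".

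The outcome scale is not settled. Analysis methods reads as change from baseline, while Primary endpoint defines the week-26 value adjusted for baseline.

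On the amount of missing data, Sample size reports that in May 2019 "the dropout rate was nearly 60" per cent.

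**The concern.** Constant imputation builds structure into the data that the fallback sequence would treat as a feature of the outcome. A patient given the own baseline value has a change of exactly 0. On the baseline-adjusted scale that patient lies exactly on the line final = baseline. A large block of such patients spoils the residual plots, and the sequence then moves to models that either set the block aside or are governed by it.

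Missing data concedes that missing-at-random may not hold, and these two scenarios are its answer. If the fallback reached decides the result, the check says little about how relapse among drop-outs would alter the treatment effect.

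**Working it through.** **Inputs from the SAP.** Reductions of 60.34 and 32.73 pp, so a difference of 27.61 pp; SD 34.5; two-sided alpha 0.05; power 85%; 60% drop-out.

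**The plan's own figures.** Exact two-sample t-test power is 0.850 at 29 per group and 0.902 at 34 per group, as stated. Inflating for drop-out gives 58/0.4 = 145 against the stated 144, and 68/0.6 = 113.3, rounded up to the stated 114. The inputs are sound for this check.

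**Difference in means, own-baseline imputation.** With missing share m in both arms, imputed patients contribute 0 change, so the expected difference is (1 − m) × completers' difference. At m = 0.6 this is 0.4 × 27.61 = 11.0 pp. The relapse assumption shows as dilution.

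**The sequence on the change scale.**
1. ANOVA: the residuals contain a spike made by the imputation.
2. Log: a change of 0 has no logarithm, and no shift removes a spike.
3. Zero-inflated Gaussian: the imputed zeros go to the zero part, so the Gaussian part compares completers. The combined mean would restore the dilution, (1 − m) × Gaussian difference, but the SAP does not say which component is reported.
4. Median: if more than half of each arm equals 0, both medians are 0 and so is their difference.

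**Simulation.** 60 patients per arm, 300 trials per setting, 58% missing per arm (35 of 60). Assumptions: baseline uniform on 5 to 30 heavy drinking days out of 30; reductions drawn with the SAP's means and SD; follow-up either unlimited or held within 0-30 days. Results in pp, own-baseline imputation:

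| Analysis | No limit | 0-30 days |
|---|---|---|
| Completers only | 28.3 | 16.5 |
| Mean change (ANOVA) | 11.8 | 6.9 |
| ANCOVA on baseline | 11.8 | 6.8 |
| Zero-inflated, Gaussian part, change | 28.3 | 16.1 |
| Median of change | 0 in 100% of runs | 0 in 100% of runs |
| Baseline-adjusted median regression | 0 in 100% of runs | 0 in 100% of runs |

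The means agree with the formula: 25/60 × 28.3 = 11.8. The Shapiro p-value for change was below 10⁻⁶ in every run.

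**Half-baseline imputation, 0-30 days.** ANOVA 6.9, Gaussian part 6.7 (only 0.8% of changes are zero), median of change 5.0. Only baseline-adjusted median regression returns exactly 0.

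**Dependence on the missing share** (0-30 days, own-baseline imputation):

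| Missing, exenatide/placebo | Mean difference, change | Median difference, change |
|---|---|---|
| 30/30% | 11.1 | 14.9 |
| 45/45% | 8.7 | 12.5 (0 in 6% of runs) |
| 58/58% | 6.9 | 0 in 100% |
| 65/51% | 2.2 | 0 in 100% |
| 70/46% | −0.9 | 0 in 94% |

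The mean responds to unequal missingness, as a relapse analysis should; the median does not. For half-baseline imputation, baseline-adjusted median regression was already 0 in 91% of runs at 45% missing per arm, and in 3% at 30%.

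**The case against.** A reader might infer that the relapse analysis must return either zero or the completers' result and so cannot test the primary finding. The SAP does not support that, for these reasons:

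- **The trigger is inferred.** Nothing states that the fallback sequence is re-run on the imputed data, and the residual check is a visual judgement. If ANOVA is kept, the scenario works as intended.
- **The order matters.** Median regression comes only after the earlier steps fail. On the change scale the zero-inflated model would be tried first, so the exact zero needs a further failure.
- **Drop-out is not missing final data.** The reported rate is pooled and dates from before recruitment closed. Under Withdrawal/Follow up, patients who withdrew after at least eight weeks were encouraged to attend the final assessment at that time. The missing share may be lower, and no per-arm figure is given.
- **The mixture has two parts.** Its combined mean keeps the relapse assumption.
- **The scale is open.** On the unadjusted week-26 value with 58% missing, the median difference was 8.6 pp and the Gaussian part 1.7 pp, neither zero nor the completers' result.
- **Half-baseline imputation is mostly unaffected**, as the figures above show.

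All of this stands as a limit on the claim. It does not remove the point. The sequence is the only model rule the SAP supplies for these outcomes, and no section exempts the imputed data. The unadjusted week-26 value is not the primary endpoint as defined. The sponsor's own revised sample size, 144 randomised for 58 evaluable, treats most randomised patients as lost to the analysis.

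**Conclusion.** The point holds conditionally. With own-baseline imputation analysed as change, the imputation itself breaks the normality check. What follows depends on choices the SAP leaves open. Reporting the Gaussian part alone removes the relapse assumption (16.1 against 16.5 pp in completers). Median regression gives exactly 0 once more than about half of the final values are missing in each arm, whatever the completers show. That share is plausible given the reported drop-out, but not established. A comparison of means gives 6.9 pp on the same simulated data, or 11.0 pp by formula at the planning values with 60% missing per arm.

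The same data could therefore yield about 0, 7 or 16 pp, depending on a visual reading of residuals that the imputation has distorted. The figures rest on an assumed baseline distribution, assumed per-arm missingness and 60 patients per arm, none of which the SAP gives. This is more than a missing detail, because following the stated sequence can empty the SAP's main check on missing-at-random. It should be corrected, but it does not show that the planned check must fail.

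**What to change.** Add to Sensitivity analysis and Missing data, before participants are divided into groups A and B (Timing of final analysis):

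- Both scenarios are analysed as the baseline-adjusted difference in mean week-26 value by linear ANCOVA, with heteroscedasticity-robust or bootstrap standard errors.
- The log, zero-inflated and median fallbacks in Analysis methods are not applied to constant-imputed data.
- The same ANCOVA is also reported on the multiply imputed data.

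The last item deals with the one small downside: if the primary analysis moves to a fallback, the sensitivity model would differ from it, and a like-for-like mean comparison is then needed. The cost is about one SAP sentence and negligible programming, with no new data.

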#### Adherence and protocol deviations

Adherence to the intervention was defined by no more than 3 missed consecutive injections, or 5 missed injections in total during the 26-week period. The un-blinded project nurses kept an individual injection schedule per patient and thereby kept track of the extent of exposure. Adherence to the intervention will be presented as a table of distribution of percentage of weeks with study medication injections in the main treatment period. Protocol deviations will be presented in a table divided into the categories: study procedure, eligibility, and randomisation. Only protocol deviations regarding "lost to follow up" and "withdrawal" will be summarized in the section named this.

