# Withdrawal/Follow up

All patients who have withdrawn from the intervention and have been included for at least eight weeks (steady-state plasma level) were encouraged to participate in the last week 26 follow-up including brain scans at the time of withdrawal. If successful, individuals will be contacted for a long-term follow-up after further 26 weeks. All other individuals e.g individuals who withdraw before eight weeks and lost to follow-up will not be contacted for a long-term follow-up. Data will be presented in a Kaplan Meyer survival curve

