# Secondary endpoints

- 1. Total alcohol consumption (gram/day) during the last 30 days, at follow up after 26 weeks of treatment adjusted for baseline. Data will be registered via the Timeline-Follow-Back-method (TLFB).
- 2. Percentage of days without any alcohol consumption during the last 30 days, at follow-up after 26 weeks of treatment adjusted for baseline (percentage points (pp)). Data will be registered via the Timeline-Follow-Back-method (TLFB).
- 3. Phosphatidylethanol (PEth) (ng/mL) at follow-up after 26 weeks of treatment, adjusted for baseline.
- 4. Penn Alcohol Craving Scale (PACS) score at follow-up after 26 weeks of treatment, adjusted for baseline.

Rigshospitalet

Statistical Analysis Plan

Edition: 1.0

EudraCT 2016-003343-11

- 5. Alcohol Use Disorders Identification Test (AUDIT) score at follow-up after 26 weeks of treatment, adjusted for baseline.
- 6. Screen for Cognitive Impairment in Psychiatry test (SCIP) score at follow-upafter 26 weeks of treatment, adjusted for baseline and week 4.
- 7. The liver parameter alanine aminotransferase (ALAT) (U/L) at follow up after 26 weeks of treatment, adjusted for baseline.
- 8. The liver parameter gamma-glutamyl transferase (GGT) (U/L) at follow up after 26 weeks of treatment, adjusted for baseline.
- 9. Mean cell volume (MCV) (fL) at follow up after 26 weeks of treatment, adjusted for baseline.
- 10. Short-Form Health Survey (SF-36) score at follow-up after 26 weeks of treatment, adjusted for baseline.
- 11. Symptom Checklist (SCL-92) score at follow-up after 26 weeks of treatment, adjusted for baseline.
- 12. Bodyweight (kg) at follow-up after 26 weeks of treatment, adjusted for baseline.
- 13. Blood pressure (mmHg) at follow-up after 26 weeks of treatment, adjusted for baseline.
- 14. Pulse (PR) at follow-up after 26 weeks of treatment, adjusted for baseline.
- 15. Waist circumference (cm) at follow-up after 26 weeks of treatment, adjusted for baseline.
- 16. Glycemic control parameters HbA1c (mmol/L) at follow-up after 26 weeks of treatment, adjusted for baseline.
- 17. Kidney function (urine albumin/creatinine ratio) at follow-up after 26 weeks of treatment, adjusted for baseline.
- 18. Drug Use Disorders Identification Test (DUDIT) score at follow-up after 26 weeks of treatment, adjusted for baseline.

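### Two sensitivity analyses do not do what they state: per-protocol is offered as the MNAR analysis, and halving alcohol-free days makes halved drinking look worse than full relapse

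*SAP*

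**What the plan says.** Under Sensitivity analysis, the SAP names three outcomes: "Sensitivity analysis is planned for the outcomes: heavy days, total alcohol intake, 0-days". Two items follow.

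- Item 1 takes dropout to mean relapse and says "we will impute the values of the missing final data for the above categories, as the baseline value and half a baselinevalue". The rule covers all three outcomes.
- Item 2 says "We assume the missing data are MNAR and will make a per protocol (PP) analysis".

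The Missing data section makes multiple imputation the main approach, concedes that MAR may not hold, and says "we will consider two realistic alternatives for the missing mechanism". The first is a return to pre-study drinking. The second is "that all non-observed individuals at 26 weeks have halved" their drinking. Per-protocol is not one of the two.

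Four other places bear on this:

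- Secondary endpoint 2 defines the alcohol-free-days outcome: "Percentage of days without any alcohol consumption during the last 30 days". Higher is better, the opposite of heavy drinking days and total intake.
- Analysis populations puts all analyses on an intention-to-treat basis among dosed patients and lists no per-protocol set.
- Adherence and protocol deviations holds the nearest thing to a per-protocol rule: "Adherence to the intervention was defined by no more than 3 missed consecutive injections", or 5 in total.
- Withdrawal/Follow up says that patients who withdrew after at least eight weeks "were encouraged to participate in the last week 26 follow-up including brain scans at the time of withdrawal".

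**The concern.** **Per-protocol as the MNAR analysis.** MNAR is a statement about outcomes that were not observed: the chance of being missing depends on the unseen drinking itself. A sensitivity analysis for it has to say something about those values. A per-protocol analysis drops patients and says nothing about them. If it is then read as a treatment effect, it relies on exclusion being unrelated to outcome, or acting alike in both arms. It therefore leaves in place the selection that item 2 says it is addressing. The SAP reports dropout of nearly 60% (Sample size), so a reader will look to these analyses for reassurance. A per-protocol result close to the multiple-imputation result could be reported as robustness to MNAR without showing it.

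**The half-baseline rule for alcohol-free days.** Halving a harmful quantity gives a milder scenario; halving a beneficial one gives a harsher one. Applied as written, the rule gives a dropout who has supposedly halved their drinking more drinking days than one who has fully relapsed. The sensitivity range for this secondary endpoint is then inverted, and a programmer following the text literally would produce it that way.

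**Working it through.** The SAP gives no figure of its own on either point, so there is none to reproduce. The checks below use its rules.

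**1. Alcohol-free days**

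Inputs: a 30-day window (Secondary endpoints); imputed values of baseline and half of baseline (Sensitivity analysis, item 1); scenarios of full reversion and halved drinking (Missing data). Let *b* be alcohol-free days at baseline. Eligibility requires at least 5 heavy drinking days, so *b* is at most 25.

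- Full reversion: *b*
- Written half rule: *b*/2
- Halved drinking, if the number of drinking days is halved: 30 − (30 − *b*)/2
- Halved drinking, if only the amount per day is halved: *b*

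Imputed alcohol-free days, with the implied drinking days in brackets:

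| *b* | Full reversion | Written half rule | Drinking days halved | Amount per day halved |
|---|---|---|---|---|
| 0 | 0 (30) | 0 (30) | 15 (15) | 0 (30) |
| 5 | 5 (25) | 2.5 (27.5) | 17.5 (12.5) | 5 (25) |
| 10 | 10 (20) | 5 (25) | 20 (10) | 10 (20) |
| 20 | 20 (10) | 10 (20) | 25 (5) | 20 (10) |
| 25 | 25 (5) | 12.5 (17.5) | 27.5 (2.5) | 25 (5) |

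Since *b*/2 < *b* for every *b* > 0, the written rule is always harsher than full reversion; the two tie only at *b* = 0. Neither reading of halved drinking gives *b*/2 at any *b* > 0.

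Shortfall per dropout against each reading:

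- Drinking days halved: 30 − (30 − *b*)/2 − *b*/2 = 15 days for every *b*, and 15/30 = 50 pp.
- Amount per day halved: *b* − *b*/2 = *b*/2. At *b* = 10 this is 5 days, and 5/30 = 16.7 pp.

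Effect on the arm difference = shortfall × difference in dropout proportion. With an assumed imbalance of 10 percentage points:

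- First reading: 50 × 0.10 = 5.0 pp.
- Second reading, *b* = 10 in both arms: 16.7 × 0.10 = 1.7 pp.
- Zero if dropout is balanced and, on the second reading, dropouts' baseline alcohol-free days are balanced too.

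The other five of the six outcome-by-scenario combinations are coherent: full baseline for all three outcomes, and half baseline for heavy days and total intake.

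**2. Per-protocol under MNAR**

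The main argument is textual. Item 2 names MNAR and answers with a population restriction; Missing data names two mechanisms and answers with imputed values. Only the latter specifies anything about the missing outcomes.

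A simple model shows that restriction can mislead. Completers stand in for a per-protocol set. From the SAP: SD 34.5 (planned there for the change in heavy drinking days) and 60% dropout, applied here to each arm. Assumed: percentage of heavy drinking days *y* normal with mean 45, clipped to 0–100; the same distribution in both arms, so no true effect; logit P(dropout) = *a* + *s*(*y* − 45)/34.5, with *a* set to give 60% dropout.

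Completer means: *s* = 0, 45.74; *s* = 0.25, 41.89; *s* = 0.5, 38.24; *s* = 1, 31.97.

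Spurious arm differences:

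- equal slopes in both arms: 0 pp
- 0.5 vs 0.25: 41.89 − 38.24 = 3.7 pp
- 1 vs 0.5: 38.24 − 31.97 = 6.3 pp
- 1 vs 0: 45.74 − 31.97 = 13.8 pp

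A variant with an unclipped normal outcome of mean 50 gave about 17 pp, in either direction, when dropout depended on outcome in one arm only. The SAP does not give the real mechanism, so these figures show only that the bias can be anything from nil to substantial.

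**The case against.** The plan is not without MNAR analyses. The baseline and half-baseline imputations are non-MAR scenarios, and for the primary endpoint both are sound. On that view item 2 is a mislabelled supplementary analysis, and because Missing data does not count per-protocol among its mechanisms, the risk of misreading is limited. This stands as a limit on scope. It does not make the label right, and it leaves two sections of one plan disagreeing on what the MNAR analysis is.

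The bias figures come from assumed models with unequal slopes and do not measure the effect of a label. That is accepted: they are illustrative.

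A per-protocol set is meant to exclude non-adherers, and the SAP does not tie it to the adherence rule. So the loss of assessments from patients who withdrew after eight weeks is a possibility, not a certainty. Those assessments also take place at withdrawal, not necessarily at week 26. This too is accepted.

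On alcohol-free days, item 1 rests on relapse, and halved drinking appears only under Missing data. Read alone, fewer alcohol-free days could be a deliberately pessimistic value. This reading fails. The same rule would give one patient half the heavy days and half the intake, yet more drinking days than at full reversion.

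Delta shifts can be called an extra analysis, since relabelling alone removes the misstatement. That is fair, but item 2 promises an MNAR analysis, and delta shifts on the planned imputation are an inexpensive way to supply one.

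**Conclusion.** Both parts hold. Per-protocol is not an MNAR analysis, and agreement between it and multiple imputation would not show robustness to MNAR. That conclusion rests on the definitions and needs no assumed model; the size of any per-protocol bias cannot be fixed from the SAP.

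The alcohol-free-days rule is wrong in direction for every baseline above zero. The error is 15 days (50 pp) or *b*/2 days per dropout, depending on how halved drinking is read. Its effect on the arm difference depends on dropout imbalance, which the SAP does not report by arm, and may be zero.

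The primary analysis, the primary endpoint's two imputation scenarios and every stated figure are untouched. This should be fixed before analysis because the rules are wrong as written, but it does not threaten the trial's main result.

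**What to change.** 1. **Per-protocol.** Call it an adherence analysis, remove the MNAR statement from it, and state its population: whether the adherence rule defines it, and whether assessments made at withdrawal are included.
2. **MNAR item.** Use the multiple imputation already planned and add arm-specific delta shifts to the imputed week-26 heavy drinking days, increasing them until the conclusion changes (the tipping point). State how shifted values outside 0–100% are handled.
3. **Alcohol-free days.** Define halved drinking on the drinking scale and say which reading is meant: 30 − (30 − *b*)/2 if drinking days are halved, or *b* unchanged if only the amount per day is halved. Use the same definition under Sensitivity analysis and Missing data.
4. **Leave the other five imputation rules as written.**

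Items 1 and 3 cost only wording. Item 2 needs modest extra programming on imputations that will exist anyway. The SAP is to be completed before participants are divided into groups A and B, so the changes should be made and dated before that step; if it has already been taken, they should be marked as later changes.
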